After screening, subjects will receive the following tests: (1) Measurement of hepatic glucose production, substrate oxidation and plasma ketone/lactate/insulin/glucagon concentrations; (2) (Measurement of whole body norepinephrine turnover with ^3H -norepinephrine infusion; (3) Measurement of heart rate variability; (4) Measurement of liver fat content with ^1H -MRS; (5) 75-grams oral glucose tolerance test (OGTT)

The studies will be performed in a random order.

After the completion of the above studies, subjects in each group will be randomized (in 2:1 ratio) to receive for 12 weeks, empagliflozin 25 mg per day (n=24) or placebo (n=12), in a double blind fashion. The drug treatment will be started (day 1) on the day of the second hepatic glucose measurement (see specific details below). On day 2, the measurement of heart rate variability and norepinephrine turnover will be repeated. Subjects will continue treatment with the drug (empagliflozin or placebo) that they received during the second hepatic glucose measurement for 12 weeks and at the end of 12 weeks, all baseline tests will be repeated.

The treatment period could be extended based upon the circumstances until the repeat studies are completed.

Tests	Baseline	Day 1-3	12 Weeks
OGTT	OGTT		OGTT
HGP	Short	Long	Short
NE	NE	NE	NE
MRI	MRI		MRI
DEXA	DEXA		
HRV	HRV	HRV	HRV

The metabolic effects of empagliflozin lasted for 2 weeks in our previous studies (7). However, Ferrannini and colleagues (40) reported that at 4 weeks, the glucose effects of empagliflozin (HGP) are attenuated while the fat effects (fat oxidation and ketone production) are enhanced. Therefore, to evaluate the long term metabolic impact of SGLT2 inhibition, we decided to extend the treatment period in the current study to 12 weeks.

Specific Methods:

Screening: Medical history and physical examination will be performed. Blood samples will be drawn for CBC, blood chemistries, lipid profile, thyroid function and HbA1c. EKG will be performed.

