Measurement of Hepatic Glucose Production with ^3H -glucose infusion (HGP – short): The rate of endogenous (primarily reflecting liver) glucose production will be measured with ^3H -glucose infusion as previously described (7). After a 10 hour overnight fast, a prime (25 $\mu\text{CiXFPG}/100$) - continuous (0.25 μCi) infusion of ^3H -glucose will be started and continued for 3 (4 in T2DM patients) hours. After 2 hours (3 hours in T2DM patients) of tracer equilibration, blood samples will be drawn from the catheter on the dorsum of the hand at 120, 130, 140, 150, 160, 170 and 180 minutes (from 180-240 minutes in T2DM patients). Plasma glucose, insulin, glucagon, GLP-1, cortisol, growth

hormone, ketones, lactate, bicarbonate and catecholamine concentrations, and ^3H -glucose specific activity will be measured. Indirect calorimetry to measure energy expenditure and substrate oxidation rates will be performed between 60-90 minutes.

Measurement of Hepatic Glucose Production With Drug Administration (HGP – Long): On the day of starting the treatment, the rate of endogenous (hepatic) glucose production will be measured with ^3H -glucose as described above with one difference. The ^3H -glucose infusion will be continued for 7 hours (8 in T2DM patients). After 2 hours of tracer equilibration (3 hours in T2DM patients), blood samples will be drawn from the catheter on the dorsum of the hand at -30, -20, -15, -10, -5 and 0 (time zero is drug ingestion time) minutes. At time zero, subjects will receive the first dose of the drug (placebo or empagliflozin 25 mg) and blood samples will be obtained from the retrogradely-placed catheter on the dorsum of the hand every 20-30 minutes for 5 hours. Plasma glucose, insulin, C-peptide, glucagon, GLP-1, cortisol, growth hormone, ketone, lactate, bicarbonate, and catecholamine concentrations, and ^3H -glucose specific activity will be measured. Urine will be collected during the equilibration period and after drug administration. Urinary volume and glucose concentration will be measured and urinary glucose excretion rate will be calculated. Indirect calorimetry to measure energy expenditure and glucose and fat oxidation will be performed 3 times through the study, from -60 to -30, from 150 to 180 and from 270 to 300 minutes. Blood will also be drawn to monitor renal function, electrolytes, glucosuria, and monitor and mitigate urinary tract infections.

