Boehringer Ingelheim Pharmaceuticals, Inc.

[name]

[contact]

For each adverse event, the investigator will provide the onset date, end date, intensity, treatment required, outcome, seriousness, and action taken with the investigational drug. The investigator will determine the expectedness of the investigational drug to the AEs as defined in the Listed Adverse Events section of the Boehringer Ingelheim's (BI's) Investigator Brochure for the Product BI Drug

Information e.g. Summary of Product Characteristics (SmPC) or Product Information (PI) for the authorised Study Drug provided by BI,

After the individual patient's end of trial: the investigator does not need to actively monitor the patient for new AEs but should only report any occurrence of cancer and trial treatment related SAEs which the investigator may become aware of by any means of communication.

Data Analysis Plan: Data Analysis and Statistical Plan: Glucosuria Induced Increase in Hepatic Glucose Production: Under steady-state postabsorptive conditions, the basal rate of endogenous (primarily reflecting hepatic) glucose appearance ($R_a = bHGP$) equals the ^3H -glucose infusion rate divided by steady state plasma ^3H -glucose specific activity. After drug (empagliflozin) administration, non-steady state conditions for ^3H -glucose specific activity prevail and the rate of whole body glucose appearance (R_a) is calculated from Steele's equation (52). The difference between HGP in empagliflozin-treated and placebo-treated subjects, in each group (i.e. NGT, IFG and T2DM), represents the increase in HGP stimulated by glucosuria.

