During the Oral-IV double tracer infusion study, only the ^{14}C -glucose which escapes the liver and non-hepatic splanchnic tissues appears in the systemic circulation, while all of the infused ^3H -glucose appears in the systemic circulation. Therefore, the difference between R_a calculated with ^3H -glucose and R_a calculated with ^{14}C -glucose represents the basal rate of hepatic plus non-hepatic splanchnic tissue glucose uptake. Thus, the basal rate of EGP will be calculated for ^3H -glucose as the ^3H -glucose infusion (dpm/min) divided by the steady-state plasma ^3H -glucose specific activity (dpm/mg). The rate of ^{14}C -glucose appearance will be calculated as the ^{14}C -glucose infusion rate (dpm/min) divided by the steady-state plasma ^{14}C -glucose specific activity (dpm/mg). The hepatic and non-hepatic splanchnic glucose uptake equals $R_{a3\text{H}-\text{glucose}}$ minus $R_{a^{14}\text{C}-\text{glucose}}$. Norepinephrine clearance rate will be calculated as ^3H -NE infusion rate (dpm/min) divided by the steady state plasma ^3H -NE radioactivity (dpm/ml) (between 12 and 20 min). Norepinephrine spill over (release) rate (pg/min), which reflects the sympathetic nervous system activity (53), will be calculated as the product of plasma norepinephrine concentration (pg/ml) and norepinephrine clearance rate (ml/min). The difference between norepinephrine spill over in empagliflozin-treated and placebo-treated subjects, in each group (i.e. NGT, IFG and T2DM), represents the effect of glucosuria on the sympathetic nervous system activity. The ratio between plasma ^3H -DHPG to ^3H -NE (between 20 to 120 minutes) will be used as an index of neuronal uptake of norepinephrine (54).

Values will be presented as mean \pm SD. Difference between means will be compared by ANOVA. Post hoc testing will be performed with the Bonferroni test.

The increase in HGP caused by glucosuria in each treatment group will be related to the change in norepinephrine spill over rate with Pearson's correlation in each treatment group. We anticipate a strong correlation between the two variables.

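### The main HGP and norepinephrine comparisons name no baseline term although each subject's baseline is measured; ANCOVA within each group would add precision for one error degree of freedom

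*Combined protocol and SAP*

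**What the plan says.** Item 6, Data Analysis and Statistical Plan, sets the HGP effect as "The difference between HGP in empagliflozin-treated and placebo-treated subjects, in each group (i.e. NGT, IFG and T2DM), represents the increase in HGP" due to glucosuria. For NE it uses the same form: "The difference between norepinephrine spill over in empagliflozin-treated and placebo-treated subjects, in each group". The test is given in one sentence, "Difference between means will be compared by ANOVA", followed by Bonferroni post hoc testing. No covariate, change score or repeated-measures term is attached to either contrast.

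Some of the wording points to a change. The plan moves to Steele's equation for the period that begins "After drug (empagliflozin) administration, non-steady state conditions for" the tracer prevail. The correlation analysis is worded as a change: "The increase in HGP caused by glucosuria in each treatment group will be related to the change in norepinephrine spill over rate". The Sample Size Calculation also speaks of an increase in HGP versus placebo.

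The baselines exist. The Study Design table lists HGP and NE at baseline, at days 1-3 and at week 12. For NE, "On day 2, the measurement of heart rate variability and norepinephrine turnover will be repeated", and for week 12, "at the end of 12 weeks, all baseline tests will be repeated". The HGP-Long study also has its own pre-drug samples, "at -30, -20, -15, -10, -5 and 0 (time zero is drug ingestion time) minutes".

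The sample size assumes 0.34 ± 0.26 mg/kg.min, with 20 empagliflozin and 10 placebo completers per group, for over 90% power at alpha below 0.05.

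**The concern.** With 10 placebo completers per group, precision is scarce. As written, an analyst could run the ANOVA on post-drug HGP or on its change from baseline, and on day-1 or week-12 data. These choices have different error variances, and the stated power holds only for a quantity whose SD is about 0.26. The plan does not say which quantity that is. Sub-study 2 is more exact: its analysis section names a change and a window of 390 to 420 minutes.

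Using each subject's own pre-treatment value as a covariate would largely remove the dependence on that choice. What is at stake is the width of the interval and the chance of detecting the effect. Bias is not at issue, because the arms are randomised.

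**Working it through.** **Inputs.** From the Sample Size Calculation: difference 0.34, SD 0.26, 20 versus 10 completers. Assumed: two-sided alpha 0.05 (sidedness is not stated), equal SD before and after, and r between 0.3 and 0.8.

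**The plan's own figure.** SE = 0.26 × √(1/20 + 1/10) = 0.26 × 0.387 = 0.101. Noncentrality = 0.34/0.101 = 3.38. With 28 df (critical t 2.048), the noncentral t gives power 0.903. The stated figure reproduces with little slack: the largest SD that keeps 0.90 is 0.261.

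**Formulas.** With level SD s:
- SD of change = s√(2(1−r))
- ANCOVA residual SD = s√(1−r²), on 27 df (critical t 2.052)
- Chance baseline imbalance inflates the variance of the adjusted difference by 1 + 1/26 on average. The ANCOVA powers below allow for it.

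**Reading 1: 0.26 is the SD of change**, so s = 0.26/√(2(1−r)).

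| r | level SD | ANCOVA residual SD | power, level | power, change | power, ANCOVA |
|---|---|---|---|---|---|
| 0.3 | 0.220 | 0.210 | 0.97 | 0.90 | 0.98 |
| 0.5 | 0.260 | 0.225 | 0.90 | 0.90 | 0.96 |
| 0.7 | 0.336 | 0.240 | 0.71 | 0.90 | 0.93 |
| 0.8 | 0.411 | 0.247 | 0.54 | 0.90 | 0.92 |

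**Reading 2: 0.26 is the SD of the level**, so s = 0.26.

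| r | SD of change | ANCOVA residual SD | power, level | power, change | power, ANCOVA |
|---|---|---|---|---|---|
| 0.3 | 0.308 | 0.248 | 0.90 | 0.79 | 0.92 |
| 0.5 | 0.260 | 0.225 | 0.90 | 0.90 | 0.96 |
| 0.7 | 0.201 | 0.186 | 0.90 | 0.99 | 0.99 |

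**Variance of the treatment estimate.**
- ANCOVA relative to change: (1+r)/2 × 27/26 = 0.779, 0.883 and 0.935 at r = 0.5, 0.7 and 0.8. That is about 22%, 12% and 7% lower.
- ANCOVA relative to level: (1−r²) × 27/26. This is below 1 only when r² > 1/27, that is, when r exceeds about 0.19.

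**95% CI half-width, Reading 1, r = 0.5/0.7/0.8 (mg/kg.min).** Level 0.21/0.27/0.33; change 0.21; ANCOVA 0.18/0.19/0.20.

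**NE spillover.** The documents give no SD or effect, so no power or half-width can be computed. The same variance ratios would apply at whatever r holds for NE.

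**The case against.** The strongest reply is that this is a preference. The planned comparison is unbiased, the power target is met without adjustment, and naming ANOVA does not exclude a baseline. The correlation with NE change needs an HGP increase for each subject, so a change must be computed anyway, and an ANOVA on change already uses the baseline. On Reading 1 the gain over change is then only about 2 to 6 points of power for r from 0.8 down to 0.5. All of this stands, and it is why the point is minor. It does not settle the matter, because the sentence that defines the HGP contrast compares HGP itself and nothing links the ANOVA to the change.

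A second reply is that r is unknown and the large losses need three things at once: levels are compared, 0.26 is the SD of change, and r is 0.7 or more. That also stands. The documents state none of the three.

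A third is that one model pooled over NGT, IFG and T2DM would cost more than a degree of freedom, since it assumes a common slope and a common residual variance. That is correct, so the fix below works within each group.

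**Conclusion.** The point holds as a minor improvement in precision and specification. No baseline term is named, the baselines are already collected, and adjustment costs one error degree of freedom. The gain over a change analysis is small at moderate to high r. The gain over a level analysis is large only when r is high, and below about r = 0.2 there is none. These sizes rest on the assumed r, equal SDs before and after, and two-sided alpha 0.05.

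A reader might infer more, in two ways.
- That the trial is underpowered, with 0.54 to 0.71 as its real power. The documents do not support this: they never commit the ANOVA to levels, and under Reading 2 a level analysis has 0.90 at every r.
- That the sample size is wrong. It reproduces at alpha 0.05. The remark about a comparison of 3 groups is ambiguous. If it meant 0.05/3, the unadjusted power would be 0.79, but the plan does not say so, and that is a separate question.

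**What to change.** Analyse HGP and NE spillover within each glycaemic group by ANCOVA with treatment and the subject's own baseline as terms. The baseline should be:
- the mean of the -30 to 0 minute values for day-1 HGP
- the baseline HGP-Short value for week-12 HGP
- the baseline NE study for NE spillover

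Report the adjusted empagliflozin-placebo difference in each group with its 95% CI. State which HGP time point and post-drug window the sample size refers to, and whether 0.26 is the SD of a level or of a change. A pooled model with treatment-by-group is optional; if it is used, state its assumptions of a common slope and a common residual variance.

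The cost is a change of analysis wording and one error degree of freedom per group analysis (28 to 27). No visit, sample or procedure changes.

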Norepinephrine turnover rate: The rate of total body norepinephrine spillover (release), which reflects total body sympathetic nervous system activity, will be measured with ^3H -norepinephrine (^3H -NE) infusion. Subjects will report to the CRC at 7 AM after a 10 hour overnight fast, and a catheter will be placed into an antecubital vein for tracer (^3H -NE) infusion. A second catheter will be placed retrogradely into a vein on the dorsum of the hand, which is placed in a heated box (60°C) for sampling of arterialized blood. The arterialized blood will be ascertained by measuring O_2 saturation (>95%). After drawing 3 baseline blood samples, a prime (3.6 μCi) -continuous (0.36 μCi) infusion of ^3H -NE will be started and continued for 2 hours. 4-6 arterialized blood samples will be drawn from the catheter on the dorsum of the hand at every 10-30 minutes. Plasma NE and 3,4-dihydroxyphenylglycol (DHPG) concentrations and ^3H -NE and ^3H -DHPG radioactivity will be measured. Previous studies (47,48) have demonstrated that this ^3H -NE infusion rate produces a steady state of plasma ^3H -NE radioactivity within 12 minutes without significant increase (<3%) in plasma ^3H -DHPG (the primary intraneuronal metabolite of norepinephrine) radioactivity. Blood will also be drawn to monitor renal function, electrolytes, glucosuria, and monitor and mitigate urinary tract infections.

Heart Rate Variability: Heart rate variability (HRV) will be measured in the morning after a 10-12 hour overnight fast. The measurement will be performed using the SphygmoCor device (AtCor Medical, Sydney, Australia) with the participant lying in the resting supine position for 10 min. This device takes into account only the normal heart beats, ignoring ectopic beats, and derives the time (SDNN and rMSSD) and frequency (LF and HF) domain parameters of the normal R-R intervals of the electrocardiogram (49). Parasympathetic nervous system (primarily represented by decreased high frequency domain [0.15-0.4 Hz] and rMSSD), and sympathetic nervous (primarily represented by decreased low frequency domain [0.04-0.15] and SDNN) system activity will be assessed before and at day 2 and week 12 of treatment with empagliflozin. Blood will also be drawn to monitor renal function, electrolytes, glucosuria, and monitor and mitigate urinary tract infections.

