In this study, HGP measurement will be done with 6,6,D2-glucose infusion and NE turnover measurement with ³H-NE infusion. A prime (4 mg/kg) continuous (0.04 mg/kg.min) infusion of 6,6-D2-glucose (Cambridge Isotopes, Boston, MA) will be started and continued to the end of the study (8 hours). After a 3-hour basal tracer equilibration period, patients will ingest empagliflozin 25 mg (n=24) or placebo (n=12). The 6,6-D2-glucose will be continued for additional 5 hours after drug ingestion. Blood samples will be drawn from the catheter on the dorsum of the hand at -30, -20, -10, and 0 (time zero is drug ingestion time) minutes. At time zero, subjects will receive the drug (placebo or empagliflozin 25 mg) and blood samples will be obtained from the retrograde-placed catheter on the dorsum of the hand every 20 minutes for 6 hours. Plasma glucose, insulin, glucagon, GLP-1, cortisol, growth hormone, ketone, lactate, and bicarbonate, concentrations, and 6,6-D2-glucose enrichment will be measured.

At -60 minutes, ³H-NE infusion will be started for 60 minutes (from -60 to 0 minutes) for the measurement of NE turnover as described above (4 blood samples are collected every 10-30 minutes between -60 and time zero). The ³H-NE infusion will be repeated at 240 minutes and 4 blood samples are collected before and after 3H NE infusion. Urine will be collected during the equilibration period and after drug administration (0 to 5 hours). Urinary volume and glucose concentration will be measured and urinary glucose excretion rate will be calculated. Indirect calorimetry to measure energy expenditure and glucose and fat oxidation will be performed 2 times through the study, from -90 to -60, from and from 210 to 240 minutes. Blood will also be drawn to monitor renal function, electrolytes, glucosuria, and monitor and mitigate urinary tract infections.

Measurement of Hepatic Glucose Production With 6,6,D2-glucose, ³H-NE infusion and glucose clamp:

HGP will be measured with 6,6,D2-glucose and NE turnover will be measured as described above with one difference. After the drug ingestion, the plasma glucose concentration will be measured every 5 minutes and variable 20% dextrose solution will be adjusted to maintain the plasma glucose concentration at the fasting level. Blood will also be drawn to monitor renal function, electrolytes, glucosuria, and monitor and mitigate urinary tract infections.

Effect of Empagliflozin on EGP and NE turnover with Pancreatic Clamp:

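### The 12–20 min window for norepinephrine clearance holds at most one scheduled draw and possibly none, and two Sub-Study 1 sampling rules do not fit the formula

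*Combined protocol and SAP*

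**What the plan says.** **Formula (Item 6, Data Analysis Plan).** NE clearance is the tracer infusion rate divided by steady-state plasma tracer radioactivity, taken over a stated window: "NE radioactivity (dpm/ml) (between 12 and 20 min". Spillover is plasma NE concentration times that clearance. The tracer DHPG/NE ratio has its own window: "between 20 to 120 minutes) will be used as an index of neuronal uptake of norepinephrine".

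**Main study (Item 6, Norepinephrine turnover rate).** The tracer runs for 2 hours. After three baseline samples, "4-6 arterialized blood samples will be drawn from the catheter on the dorsum of the hand at every 10-30 minutes". Earlier work is cited for a steady state of plasma tracer "radioactivity within 12 minutes without significant increase (<3%) in plasma" DHPG radioactivity. No clock times are given for the draws.

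**Sub-Study 1 (drug-administration and pancreatic-clamp visits).** The first tracer infusion runs for 60 minutes, from -60 to 0, and "4 blood samples are collected every 10-30 minutes between -60 and time zero". For the second, the "infusion will be repeated at 240 minutes and 4 blood samples are collected before and after 3H NE infusion". Its length is not stated. The glucose-clamp visit takes its NE method by reference to the drug-administration visit.

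**The concern.** The sampling rule and the analysis window were written separately, and nothing ties a draw to the window. A site can follow the sampling section exactly and leave the analyst with no radioactivity value between 12 and 20 minutes. Clearance and spillover then cannot be computed as written, and a different window would have to be chosen after the data exist. If one draw does fall in the window, the formula works, but a single missed or failed sample removes that visit's value, and the plan has no fallback.

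Spillover is the measure of sympathetic activity in Specific Aim 2. The plan compares it between empagliflozin and placebo in each group and correlates its change with the change in hepatic glucose production. Sub-Study 1 also needs the pre-drug and post-drug values to be measured in the same way, and its sampling text describes the two infusions differently.

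**Working it through.** The plan gives no figure to reproduce here. The check compares its timing rules, counting minutes from the start of the tracer infusion.

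**Inputs.** Window: 12 to 20 min (Data Analysis Plan). Gap between draws: 10 to 30 min. Main study: 4–6 draws in 120 min (Norepinephrine turnover rate). Sub-Study 1, first infusion: 4 draws in 60 min.

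**1. Most draws the window can hold.** Its width is 20 − 12 = 8 min. If a draw falls at time t ≥ 12, the next is at t + 10 ≥ 22, which is past 20. The maximum is therefore one.

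**2. Fewest draws.** Compliant schedules, with both window edges included:

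| Draw times (min) | Gaps | Draws in 12–20 |
|---|---|---|
| 10/20/30/60/90/120 | 10–30 | 1 (edge) |
| 20/40/60/80/100/120 | 20 | 1 (edge) |
| 15/30/45/60 (60-min infusion) | 15 | 1 |
| 30/60/90/120 | 30 | 0 |
| 24/48/72/96/120 | 24 | 0 |
| 10/30/60/90/120 | 20–30 | 0 |

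The last row shows that even an early first draw does not guarantee a value. Enumerating all whole-minute schedules with a first draw at 10–30 min found none with two draws in the window, and found empty windows at every draw count:

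- 120 min, 4 draws: 110,691 of 194,481
- 120 min, 5 draws: 2,092,191 of 3,812,280
- 120 min, 6 draws: 20,865,809 of 44,007,348
- 60 min, 4 draws: 3,795 of 10,626

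These counts show that such schedules exist. They are not probabilities.

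**3. Sub-Study 1, pre-drug against post-drug.** Before drug, the window is -60 + 12 = -48 to -60 + 20 = -40 min, and the four samples lie within the infusion. After drug, the infusion starts at 240 min, so the same window is 252 to 260 min. The samples are instead described as before and after the infusion. Taken literally, none is drawn at tracer steady state, so the formula has no denominator and the two measurements do not match.

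**4. DHPG/NE window.** A 20–120 min window needs 120 min of infusion. Sub-Study 1's first infusion lasts 60 min, so only 20–60 min can apply.

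**The case against.** **The sections do not contradict each other.** This stands. Several natural schedules satisfy both, and staff who know that steady state is reached within 12 min may well draw at 15 or 20. A reader might infer that spillover will be missing for many subjects. The documents do not support that: an empty window is permitted, not forced.

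**One draw is enough.** This also stands as far as the formula goes. It asks for a steady-state value, not for a mean of two. Having at most one draw is a weakness against missed samples, not an error.

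**The glucose draw times.** A reader might infer that NE in Sub-Study 1 is drawn with the pre-drug glucose samples, taken from the "hand at -30, -20, -10, and 0 (time zero is drug ingestion time) minutes". Those fall 30, 40, 50 and 60 min after tracer start, so the window would be empty before drug. The documents do not support this. NE sampling has its own sentence, NE is not among the analytes listed for those draws, and the long glucose-production study in the main protocol does list catecholamines. The pancreatic-clamp set (-30, -20, -10, -5, 0) has 5-min gaps and does not meet the NE spacing rule. The point does not rely on these times.

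**Before and after is loose wording.** Plausibly so. The main study draws baseline samples before the tracer, the infusion is said to be repeated, and Sub-Study 1's introduction places this measurement 5 hours after drug (300 min). Together these suggest sampling from 240 to 300 min. That is an inference, and the text should say it.

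**Fixing one draw inside the window would be enough.** It would close the empty-window gap. It would not cover a missed draw, the post-drug wording or the DHPG/NE window.

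**Conclusion.** The point holds as a mismatch between sampling and analysis rules that should be corrected. As written, at most one of the 4–6 draws (4 in Sub-Study 1) can inform clearance, and a compliant schedule may supply none. Sub-Study 1's post-drug wording, read literally, gives no steady-state value, and the DHPG/NE window cannot apply to its 60-min infusion.

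The reach is limited. The sample size is based on hepatic glucose production, so no sample-size figure changes. The loss of precision from relying on one draw cannot be quantified, because the documents give neither an assay CV nor an SD for spillover.

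The conclusion assumes that the analysis minutes count from the start of the tracer infusion, which agrees with the cited steady state within 12 min. It also assumes that the repeat infusion is meant to mirror the first.

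**What to change.** 1. **State draw times from infusion start**, within the 10–30 min rule, with one draw inside 12–20 min at every infusion. Examples for the main study: 15/45/75/105 (4 draws), 15/40/65/90/120 (5) or 15/30/50/70/95/120 (6). For Sub-Study 1: 15/30/45/60, that is -45/-30/-15/0 and 255/270/285/300 min.
2. **Reword the post-drug sampling** in the drug-administration and pancreatic-clamp visits, so that the samples are taken during the repeat infusion at the same times after its start as the pre-drug samples. State the length of that infusion.
3. **Prespecify one clearance definition** for all groups, arms and visits: mean tracer NE radioactivity over all draws from 12 min to the end of infusion. Report the 12–20 min value as a sensitivity analysis, and do not switch definitions on the basis of the data.
4. **State the Sub-Study 1 DHPG/NE window** as 20 min to the end of infusion.

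**Cost.** No added NE draws or visits. Some NE draws may not coincide with glucose draws and so may need separate samples. The 4-draw main-study example ends at 105 min (15 + 3 × 30), not 120. Under these schedules 3, 4 or 5 draws (main study, 4, 5 or 6 draws) and 3 draws (Sub-Study 1) fall after 20 min for the DHPG/NE ratio. Item 3 relies on steady state persisting beyond 20 min, which the sensitivity analysis checks.
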